	Conducted: When "HBs antibody test" in the survey form was
	conducted (If "conducted" was not checked but the test results were
HBs antibody test	provided, it should be regarded as "conducted")
	Not conducted: When "HBs antibody test" in the survey form was
	not conducted
	Unknown/not provided: other than the above
	Conducted: When "HBc antibody test" in the survey form was
HBc antibody test	conducted (If "conducted" was not checked but the test results were
	provided, it should be regarded as "conducted")

Data name	Derivation and calculation methods
	Not conducted: When "HBc antibody test" in the survey form was
	not conducted
	Unknown/not provided: other than the above
	Conducted: When "HBV-DNA quantification assay" in the survey
	form was conducted (If "conducted" was not checked but the assay
HBV-DNA	results were provided, it should be regarded as "conducted")
quantification assay	Not conducted: Not conducted: When "HBV-DNA quantification
	assay" in the survey form was not conducted
	Unknown/not provided: other than the above
	Conducted: When either of "Tuberculin test" or "IGRA" was
	conducted (If "conducted" was not checked but the results were
Tuberculin test or IGRA	provided, it should be regarded as "conducted")
Tuberculin test of IGRA	Not conducted: When neither "Tuberculin test" nor "IGRA" was
	conducted
	Unknown/not provided: other than the above
	When the first administration date of Humira is 1 and a day before
	the first administration date is -1, the patients who underwent chest X
Chest X ray test	ray test should have a record in which the chest X ray test was
	conducted between -90 and 1. Of note, the data in the survey form
	shall be used.
	When the first administration date of Humira is 1 and a day before
	the first administration date is -1, the patients who underwent
Chest CT test	thoracic CT test should have a record in which the CT test was
	conducted between -90 and 1. Of note, the data in the survey form
	shall be used.
	When the first administration date of Humira is 1 and a day before
	the first administration date is -1, the patients who underwent any
Other imaging	other imaging should have a record in which the imaging was
	conducted between -90 and 1. Of note, the data in the survey form
	shall be used.
	Conducted: When either "chest X ray" or "CT test" in the survey
Chest X ray or CT test	form was conducted (If "conducted" was not checked but the test
	results were provided, it should be regarded as "conducted")
	Not conducted: other than the above
Presence/absence of prior	The drug names described in "prior-medication history for colitis
medications	ulcerative" in the survey form should be regarded as the prior

Data name	Derivation and calculation methods
	medications. Note that when a drug code is null, it is not regarded as a prior medication. When prior-medication data are contained in the survey form, it
Presence/absence of prior medication (aminosalicylic acid	when prior-medication data are contained in the survey form, it should be classified as "with prior medication". When there is no description of "presence/absence of prior medications" in the survey form or the assessment is impossible, it should be classified as "unknown/not provided", and other cases are "without prior medications". Refer to "171218 drug list_UC". If prior-medication data of the applicable drug code are provided in the survey form, or if an aminosalicylic acid drug in the survey form is checked, regard the case as "with aminosalicylic acid". Others are "without
drug)	aminosalicylic acid". Refer to "171218 drug list UC". If prior-medication data of the
Presence/absence of prior medication (corticosteroids)	applicable drug code are provided in the survey form, or if corticosteroids in the survey form is checked, regard the case as "with corticosteroids". Others are "without corticosteroids".
Presence/absence of prior medication (azathioprine)	Refer to "171218 drug list_UC". If prior-medication data of the applicable drug code are provided in the survey form, or if azathioprine in the survey form is checked, regard the case as "with azathioprine". Others are "without azathioprine".
Presence/absence of prior medication (6-mercaptopurine)	Refer to "171218 drug list_UC". If prior-medication data of the applicable drug code are provided in the survey form, or if 6-mercaptopurine in the survey form is checked, regard the case as "with 6-mercaptopurine". Others are "without 6-mercaptopurine".
Presence/absence of prior medication (azathioprin & 6-mercaptopurine)	Refer to "171218 drug list_UC". If prior-medication data of the applicable drug code are provided in the survey form, or if azathioprin and 6-mercaptopurine in the survey form are checked, regard the case as "with azathioprin & 6-mercaptopurine". Others are "without azathioprin & 6-mercaptopurine".
Presence/absence of prior medication (tacrolimus & ciclosporin)	Refer to "171218 drug list_UC". If prior-medication data of the applicable drug code are provided in the survey form, or if tacrolimus & ciclosporin in the survey form is checked, regard the case as "with tacrolimus & ciclosporin". Others are "without tacrolimus & ciclosporin".
Presence/absence of	Refer to "171218 drug list_UC". If prior-medication data of the

Data name	Derivation and calculation methods
prior medication	applicable drug code are provided in the survey form, or if antibiotics
(antibiotics)	in the survey form is checked, regard the case as "with antibiotics".
	Others are "without antibiotics".
	When any items other than biological products in the survey form are
	checked, and when prior medication data on the drug code applicable
Presence/absence of	to the drug other than aminosalicylic acid drug, corticosteroids,
prior medication (others)	azathioprine, 6-mercaptopurine, tacrolimus, ciclosporin and
	antibiotics are included in reference to "171218 drug list_UC",
	regard it as "with others". Other cases are "without others".
Presence/absence of	Refer to "171218 drug list_UC". If prior-medication data of the
	applicable drug code are provided in the survey form, or if Infliximab
prior medication (Infliximab)	in the survey form is checked, regard the case as "with Infliximab".
(IIIIIXIIIIau)	Others are "without Infliximab".
	When 'biological products' is checked in the survey form, and when
Presence/absence of	prior-medication data of the drug codes other than Infliximab are
prior medication (other	provided in the survey form in reference to "171218 drug list_UC",
biological products)	regard the case as "with other biological products". Others are
	"without other biological products".
	The cases with either "with prior medication (Infliximab)" or "with
	prior medication (other biological products)" are regarded as "with a
Presence/absence of	treatment history with biological products". Others are "without a
treatment history with	treatment history with biological products".
biological products	As for presence/absence of the history by 'detailed classification
biological products	"with" biological products', if the applicable data among
	"Infliximab" and "other biological products" are contained, the case
	is regarded as "with" the history. Others are "without" the history.
	When the description is made in "Prior treatment for colitis ulcerative
	(including surgery)" of the survey form, regard it as a prior treatment.
Dungan og/ohannon of	When prior-treatment data are contained in the survey form, it should
Presence/absence of prior treatment	be classified as "with prior treatment". When there is no description
	of "presence/absence of prior treatment" in the survey form or the
	assessment is impossible, it should be classified as "unknown/not
	provided", and other cases are "without prior treatment".
Draganaa/ahaanaa af	Surgery should be selected if the checkbox of prior treatment
Presence/absence of	(surgery) in "prior treatment for colitis ulcerative (including
prior treatment (surgery)	surgery)" is checked and if any prior treatment considered as surgery

Data name	Derivation and calculation methods
	is included in "[Humira UC] Conversion data provided for analysis".
	When the data applicable to surgery are contained, regard it as "with
	surgery". Others are "without surgery".
	If "leukocytapheresis" in "prior treatment (including surgery) for
Presence/absence of	colitis ulcerative" is checked and it is not applicable to with prior
prior treatment	treatment (surgery) in the survey form, it shall be classified into
(leukocytapheresis)	"with leukocytapheresis". Other cases are "without
	leukocytapheresis".
	If "enteral nutrition therapy" in "prior treatment (including surgery)
Presence/absence of	for colitis ulcerative" is checked and it is not applicable to with prior
prior treatment (enteral	treatment (surgery) in the survey form, it shall be classified into
nutrition therapy)	"with enteral nutrition therapy". Other cases are "without enteral
	nutrition therapy".
Presence/absence of	If "intravenous nutrition therapy" in "prior treatment (including
	surgery) for colitis ulcerative" is checked and it is not applicable to
prior treatment	with prior treatment (surgery) in the survey form, it shall be classified
(intravenous nutrition	into "with intravenous nutrition therapy". Other cases are "without
therapy)	intravenous nutrition therapy".
Presence/absence of	If "other therapy" in "prior treatment (including surgery) for colitis
	ulcerative" is checked and it is not applicable to with prior treatment
prior treatment (other	(surgery) in the survey form, it shall be classified into "with other
therapy)	therapy". Other cases are "without other therapy".
	Concomitant medications should the data satisfying the following
	rules: Note that when a drug code is null, it is not regarded as a
	concomitant medication.
	When concomitant-medication data are contained in the survey form,
	it should be classified as "with concomitant medications". When
	there is no description of "presence/absence of prior/concomitant
Presence/absence of	medications" in the survey form or the assessment is impossible, it
concomitant medication	should be classified as "unknown/not provided", and other cases are
	"without concomitant medications".
	◆ Data with drug names in "the administration status of
	prior/concomitant medications for colitis ulcerative", "the
	administration status of other concomitant medication" of the survey
	form.

Data name	Derivation and calculation methods
Data name	 Derivation and calculation methods When the year and month are described for the first administration date of the concomitant medication, impute "1" for the "date". When the year is described for the first administration date of the concomitant medication, impute "1" each for the "month" and "date". When the year and month are described for the final administration date of the concomitant medication, impute the month's final date for the date. When the year is described for the final administration date of the concomitant medication, impute "12" for the month and "31" for the date. When the final administration of concomitant medication < the first administration date of Humira, and/or when the final administration date of Humira < the first administration date of concomitant medication. If the above imputing methods do not help add the date (the first administration date or the final administration date is not provided, etc.), or if the first administration date of concomitant medication are reversed, it should be regarded as a
	 Data with drug names in "priortreatment history for colitis ulcerative" of the survey form When the year and month are described for the first administration date of the prior medication, impute "1" for the "date". When the year is described for the final administration date of the prior medication, impute "1" each for the month and the date. If the final administration date of the prior medication ≥ the first administration date of Humira, regard it as a concomitant medication. If the above imputing methods do not help add the date, the final administration date of the prior medication shall be unknown and the case should not be regarded as a concomitant medication.

Data name	Derivation and calculation methods
	◆ Data with a drug name in "administration status of
	anti-tuberculosis drug" of the survey form
	When the year and month are described for the first
	administration date of anti-tuberculosis drug, impute "1" for the "date".
	When the year is described for the first administration date of
	anti-tuberculosis drug, impute "1" each for the "month" and "date".
	When the year and month are described for the final
	administration date of anti-tuberculosis drug, impute the
	month's final date for the date.
	When the year is described for the final administration date of
	anti-tuberculosis drug, impute "12" for the month and "31" for the date.
	When the final administration of anti-tuberculosis drug < the
	first administration date of Humira, and/or when the final
	administration date of Humira < the first administration date of
	anti-tuberculosis drug, exclude the case from the calculation for
	concomitant medication. If the above imputing methods do not
	help add the date (the first administration date or the final
	administration date is not provided, etc.), or if the first
	administration date and the final administration date of
	anti-tuberculosis drug are reversed, it should be regarded as a concomitant medication.
	concomitant medication.
	('Clear' refers to a condition where no ambiguous expressions
	like "around", "in the middle", etc. are included and a number
	of figure only is provided.)
Presence/absence of	Refer to "171218 drug list_UC". If concomitant-medication data of
concomitant medication	the applicable drug code are provided in the survey form, regard the
(aminosalicylic acid	case as "with aminosalicylic acid". Others are "without
drug)	aminosalicylic acid".
Presence/absence of	Refer to "171218 drug list_UC". If concomitant-medication data of
concomitant medication	the applicable drug code are provided in the survey form, regard the
(corticosteroids)	case as "with corticosteroids". Others are "without corticosteroids".
Presence/absence of	Refer to "171218 drug list_UC". If concomitant-medication data of

Data name	Derivation and calculation methods
concomitant medication	the applicable drug code are provided in the survey form, regard the
(azathioprine)	case as "with azathioprine". Others are "without azathioprine".
Presence/absence of concomitant medication (6-mercaptopurine) Presence/absence of concomitant medication	Refer to "171218 drug list_UC". If concomitant-medication data of the applicable drug code are provided in the survey form, regard the case as "with 6-mercaptopurine". Others are "without 6-mercaptopurine". Refer to "171218 drug list_UC". If concomitant-medication data of the applicable drug code are provided in the survey form, regard the
(azathioprine &	case as "with azathioprine & 6-mercaptopurine". Others are "without
6-mercaptopurine) Presence/absence of concomitant medication (tacrolimus & ciclosporin)	azathioprine & 6-mercaptopurine". Refer to "171218 drug list_UC". If concomitant-medication data of the applicable drug code are provided in the survey form, regard the case as "with tacrolimus & ciclosporin". Others are "without tacrolimus & ciclosporin".
Presence/absence of	Refer to "171218 drug list UC". If concomitant-medication data of
concomitant medication (antibiotics)	the applicable drug code are provided in the survey form, regard the case as "with antibiotics". Others are "without antibiotics".
Presence/absence of concomitant medication (others)	When concomitant-medication data on the drug code applicable to the drug other than aminosalicylic acid drug, corticosteroids, azathioprine, 6-mercaptopurine, tacrolimus, ciclosporin and antibiotics are included in reference to "171218 drug list_UC", regard it as "with others". Other cases are "without others".
Presence/absence of administration of anti-hepatitis B virus agent	If the following drug codes are included in the survey form, regard the case as "with administration of an anti-hepatitis B virus agent". Others are "without administration of an anti-hepatitis B virus agent". Entecavir (Baraclude): 6250029 Tenofovir (Tenozet, Viread): 6250024 Adefovir (Hepsera): 6250026 Lamivudine: 6250006, 6250020
Presence/absence of concomitant therapy	It should be described in "non-medicinal treatment/concomitant therapy (including surgery) for colitis ulcerative" of the survey form. The data from the first administration date to the final administration date of Humira will be calculated. Such data are also subject to calculation even if the first/final administration dates of concomitant treatment are not unknown. (Only when the days are not overlapped with the administration

Data name	Derivation and calculation methods
	period of Humira, they shall be excluded from the calculation.) When
	concomitant-therapy data are contained in the survey form, it should
	be classified as "with concomitant therapy". When "presence/absence
	of prior/concomitant medications" is not provided in the survey form
	or the assessment is impossible, it should be classified as
	"unknown/not provided", and other cases are "without concomitant
	therapy".
	Surgery should be selected when the 'surgery' checkbox of
	non-medicinal treatment/concomitant therapy name is checked in
D /1 C	"non-medicinal treatment/concomitant therapy for colitis ulcerative
Presence/absence of	(including surgery)" and when any concomitant therapy considered
concomitant therapy	as surgery is included in "[Humira UC] Conversion data provided for
(surgery)	analysis".
	When the data applicable to surgery are contained, regard it as "with
	surgery". Others are "without surgery".
	If "leukocytapheresis" in "non-medicinal treatment/concomitant
Presence/absence of	therapy (including surgery) for colitis ulcerative" is checked and it is
concomitant therapy	not applicable to with concomitant therapy (surgery) in the survey
(leukocytapheresis)	form, it shall be classified into "with leukocytapheresis". Other cases
	are "no leukocytapheresis".
	If "enteral nutrition therapy" in "non-medicinal
Presence/absence of	treatment/concomitant therapy (including surgery) for colitis
concomitant therapy	ulcerative" is checked and it is not applicable to with concomitant
(enteral nutrition	therapy (surgery) in the survey form, it shall be classified into "with
therapy)	enteral nutrition therapy". Other cases are "no enteral nutrition
	therapy".
	If "intravenous nutrition therapy" in "non-medicinal
Presence/absence of	treatment/concomitant therapy (including surgery) for colitis
concomitant therapy	ulcerative" is checked and it is not applicable to with concomitant
(intravenous nutrition	therapy (surgery) in the survey form, it shall be classified into "with
therapy)	intravenous nutrition therapy". Other cases are "no intravenous
	nutrition therapy".
Presence/absence of	If "other therapy" in "non-medicinal treatment/concomitant therapy
concomitant therapy	(including surgery) for colitis ulcerative" is checked and it is not
(other therapy)	applicable to with concomitant therapy (surgery) in the survey form,
(other therapy)	it shall be classified into "with other therapy". Other cases are "no

Data name	Derivation and calculation methods
	other therapy".
Tuberculosis test	Conducted: when both "Tuberculin test or IGRA" and "Chest X ray
	or CT test" were conducted
	Not conducted: other than the above
	Conducted: when "HBV-DNA quantification assay" in the survey
Hepatitis B test	form was conducted, or
	when the results are negative in HBs antigen test, HBs antibody test,
	and HBc antibody test.
	Not conducted: other than the above

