	of the year, impute the first administration date of the next record - 1 day for the final administration date.
	Of note, if the final administration date is provided in the record where the final administration date of Humira has been identified according to the above rule and the "continued" checkbox is checked, follow the below:
	 If the described final administration date > the final administration date imputed according to the above rule, select the imputed final administration date as the final administration date of Humira for the patient. If the described final administration date <= the final administration date imputed according to the above rule, select the described final administration date as the final administration date of Humira for the patient.
	If the first administration date of Humira + 364 days < the final administration date of Humira imputed according to the above rule, select the first administration date of Humira + 364 days as the final administration date of Humira.
Days to the final administration date of Humira	The final administration date of Humira - the first administration date of Humira + 1
Administration status (dosage and administration)	Sort the data by the first administration date provided in "the administration status of Humira" in the survey form and aggregate the administration status (dosage and administration) according to the following rules: • If all the following [1] to [4] are satisfied, aggregate the data as "160mg→80mg→40mg once every two weeks and no changes thereafter". • If none of the following [1] to [4] is satisfied Aggregate as "others". [1] 1st administration: as a patient with a dose of 160mg

Data name	Derivation and calculation methods
	[2] 2nd administration: as a patient with a dose of 80mg
	[3] 3rd administration and thereafter: the dosing
	frequency "once every 2 weeks" is checked in the
	survey form, and a patient with a dose of 40mg
	* If the patient receives the third administration and
	thereafter, all the administration status should be the
	condition as shown in [3].
	[4] Patients who did not have a washout period for 30
	days or longer.
	If the administration status (dose and administration) is categorized
	in "others", follow the rules below to find the reason for the change
	in dose/dosing frequency.
	• 1st dose: "a reason for other than 160mg (a dose) or in the
	case of self-administration" in the survey form.

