	When "smoking" is checked among the items for smoking history in
	the survey form, or when any descriptions are made in the smoking
	period of "smoking", they should be classified as "smoking". When
Detailed classification of	"in the past" is checked or any descriptions are made in the smoking
	period "in the past" in patients who are not classified as "smoking",
smoking history	the case should be classified as "only in the past (not smoking now)".
	When "with smoking" is checked but nothing is checked in the
	detailed classification, or when "unknown" is checked, they should
	be "unknown".
Patients with dosing	Patients other than those who satisfied [1] to [4] of "Administration
deviation of Humira	status (dosage and administration)"
Presence/absence of	When "Self-administration" in the "Administration status of Humira"
self-administration	column is checked at least once, the case should be classified as
	"with" self-administration. Others are "without" self-administration.

Data name	Derivation and calculation methods
	When both "administration by physician" and "self-administration"
	are checked, the case should be "with self-administration".
	When "with" self-administration error is checked in the survey form,
	it should be classified as "with" the error. When "without" is
D / 1 C	checked, it should be "without" the error.
Presence/absence of	When some details are provided along with the onset date in the
self-administration error	self-administration error column irrespective of a check on
	"with"/"without", it should be regarded as "with" the error.
	If nothing is described there, it should be "unknown/not provided".
	It should be identified based on the sex in the patient's information of
G.	the survey form. When multiple items are checked or data without a
Sex	description are included, the case should be classified as
	"unknown/not provided".
	It should be identified based on pregnancy/nursing in the patient's
	information of the survey form. When multiple items are checked or
D / ·	data without a description are included even if the sex has been
Pregnancy/nursing	selected as "woman", the case should be classified as "unknown/not
	provided". If the sex is not "woman" even though a description has
	been made for this item, it is excluded from the calculation.
	It should be identified based on the race in the registration form.
Race	When multiple items are checked or data without a description are

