10.3. Effectiveness analysis

Data name	Derivation and calculation methods
General improvement	Use what has been provided in "general improvement rate (primary
rate	physician's assessment" of the survey form.
	Partial Mayo score + endoscopic finding score
Mayo score	* Only the survey forms with all the scores assessed are calculated (if any
	unassessed scores are included, they are excluded from calculation)
Remission of Mayo	It should be calculated as 1 or less if the Mayo score is 2 or below and a
score	sub-score.
	Stool frequency score, rectal bleeding score and physician's global
Dontiel Mayo goons	assessment
Partial Mayo score	* Only the survey forms with all the scores assessed are calculated (if any
	unassessed scores are included, they are excluded from calculation)
Remission of partial	It should be calculated as 1 or less if the partial Mayo score is 2 or below
Mayo score	and a sub-score.
	Partial Mayo score at every assessment decreases by 2 points or more and
	by 30% or more in comparison to the partial Mayo score when
Improvement of	administration was started. In addition, at least one of the following
partial Mayo score	conditions shall be met.
(responder)	•Rectal bleeding score has been decreased by at least 1 point since the
	administration was started.
	• Rectal bleeding score is ≤1.
Endoscopy results	Use what has been provided in "endoscopic findings" of the survey form.

11. How to stratify data

Data	How to stratify
Dosage and	160mg→80mg→40mg once every two weeks and no changes thereafter,
administration	other
	The first administration to <week (1-28="" 4="" administration,="" days)<="" of="" td=""></week>
	≥Week 4 of administration and <week (29-56="" 8="" administration="" days)<="" of="" td=""></week>
	≥Week 8 of administration and <week (57-168="" 24="" administration="" days)<="" of="" td=""></week>
	≥Week 24 of administration and <week (169-336<="" 48="" administration="" of="" td=""></week>
Dose period	days)
	≥Week 48 of administration and ≤Week 52 of administration (337-365
	days)
	Unknown
	* when the first administration is counted as 1.
	≥1 and ≤4,
D	≥5 and ≤12,
Dosing frequency	≥13 and ≤24,
	≥25
	≥40mg and ≤500mg,
Total dose	≥501mg and ≤1000mg,
	≥1001mg
Reason for	Development of adverse event, lack of effectiveness, patient's wish, no
discontinuation	visit, others, multiple answers are acceptable
Reason for	Treatment/surgery, pregnancy, concern about the onset of adverse events,

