Note: After all patients' data are displayed, display "1" at the applicable column. If not applicable, leave the column blank. For "Data credibility not confirmed" in the "reason for exclusion from the safety analysis", display the breakdown. If more than one category for the breakdown exists in a patient, display them in a comma-delimited manner.

"1.4 A list of patients (adverse event + search flag)"

Patients for analysis: patients whose survey form was locked

Analysis objective: to show a list of background information per patient, adverse events and administration status by using analysis data.

Analysis items: case number, sex, age, body weight, duration of illness, adverse event (presence/absence of adverse event, safety

Patients with adverse events not in the analysis period, SOC code, System Organ Class, PT code, name of disease (MedDRA PT), adverse events reported by physician, onset date, days from the first administration to the onset, seriousness, causality, outcome, outcome confirmation date, days to the outcome confirmation), general improvement rate, administration status of Humira (the first administration date, the final administration date, days of administration, the initial dose, the maximum dose), presence/absence of complication, presence/absence of medical history, hepatitis B virus test (HBs antigen, HBs antibody, HBc antibody, HBV-DNA quantitative assay, hepatitis B test), with/without administration of anti-hepatitis B virus agent, tuberculosis (Tuberculin test, QuantiFERON test, T-spot test, chest X ray test, Thoracic CT test, other imaging, tuberculosis test), search flags (patients in the safety analysis group, patients in the effectiveness analysis group, discontinued patients, death cases, pediatrics, the elderly, pregnant, nursing, liver disorder, renal disorder, patients with hepatitis B viral infection, patients with an infection, patients with cytomegalovirus infection, patients with tuberculosis, patients with malignant tumour, patients with administration site reaction, patients with autoimmune disease, patients with pancytopenia, patients with demyelinating disease, patients with cardiac failure congestive, patients with interstitial pneumonia, patients deviated from the administration of Humira, patients with self-administration error, patients with AAA measured, contraindication)

Note: Follow "12.5 Assessment period for general improvement rate" to display the general improvement rate.

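### SAP 10.1 reserves the dosing class 'others' for patients who meet none of four conditions, so patients who miss one to three have no class in Table 1.5 and no reason in Table 1.5.1

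*SAP*

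**What the plan says.** SAP 10.1 (General), under Administration status (dosage and administration), lists four conditions:

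- [1] the first dose is 160 mg;
- [2] the second dose is 80 mg;
- [3] the third and all later doses are 40 mg once every two weeks;
- [4] there is no washout of 30 days or longer.

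The standard class is given by "If all the following [1] to [4] are satisfied, aggregate the data as" the labelled regimen. The other class is given by "If none of the following [1] to [4] is satisfied". No rule covers a patient who meets some of the conditions but not all.

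The next item in SAP 10.1, the reason for change in dose or dosing frequency, depends on the same class. It opens "If the administration status (dose and administration) is categorized" as 'others', and only then directs the programmer to the reasons recorded for the first, second, and third and later doses.

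Two outputs in SAP 13.1 use this classification:

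- Table 1.5 counts patients per class as defined in 10.1, with percentages of the analysis group, for both the safety and effectiveness groups.
- Table 1.5.1 covers the safety group. It selects the patients classed as 'others' and lists their reasons, and its note points back to the reason rule in 10.1.

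**The concern.** A two-class variable needs a second class that is the negation of the first. The negation of 'all four met' is 'at least one not met'. The SAP states 'none met', which is much narrower.

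The gap falls on ordinary patients. Take someone who receives 160 mg, then 80 mg, has no gap of 30 days, and then has the maintenance interval changed. This patient fails only [3] and so is neither standard nor 'others'. Condition [4] makes it sharper: everyone without a washout of 30 days or longer meets [4], so none of them can be 'others', whatever doses they were given.

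At stake are the completeness of Table 1.5 and the content of Table 1.5.1, which is the output meant to show why physicians departed from the regimen.

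**Working it through.** The documents state no figure on this point, so there is none to reproduce. The check is one of logic.

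**Step 1: patterns.** Each condition is met or unmet, giving 2^4 = 16 patterns. The number with k conditions unmet is C(4, k).

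| Conditions unmet | Patterns | Class as written | Class if 'others' means at least one unmet |
|---|---|---|---|
| 0 | 1 | standard | standard |
| 1 | 4 | none | others |
| 2 | 6 | none | others |
| 3 | 4 | none | others |
| 4 | 1 | others | others |

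As written, 1 pattern is standard, 1 is 'others', and 4 + 6 + 4 = 14 have no class. None of the four single departures reaches 'others'. With the complement, 1 is standard, 15 are 'others' and 0 are unclassed. These are counts of patterns, not of patients.

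**Step 2: patients.** For one analysis group let

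- N = patients in the group;
- D = those with at least one condition unmet, which is the dosing-deviation definition in SAP 10.1;
- G = those among D with a washout of 30 days or longer (condition [4] unmet);
- F = those with all four unmet, which is 'others' as written.

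The rows of Table 1.5 sum to (N − D) + F, so the shortfall is N − (N − D) − F = D − F. Failing all four includes failing [4], so 0 ≤ F ≤ G. Hence

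D − G ≤ shortfall ≤ D.

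The documents give neither D nor G, so no patient count follows. With the complement, the rows sum to (N − D) + D = N and the shortfall is 0.

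**Step 3: what the rest of the SAP assumes.**

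| Place | Rule | Agrees with |
|---|---|---|
| SAP 10.1, standard class | all four met | – |
| SAP 10.1, 'others' | none met | neither complement nor partition |
| SAP 10.1, Patients with dosing deviation of Humira | "Patients other than those who satisfied [1] to [4] of" the same item | complement |
| SAP 11, Dosage and administration | "160mg→80mg→40mg once every two weeks and no changes thereafter", and other; no residual row | complement |
| SAP 10.1, reason for change | separate look-ups for the first, second and later doses | complement: useful for patients who depart at one step |
| SAP 10.1, Tuberculosis test (also needs conditions jointly) | "Not conducted: other than the above" | shows the form the SAP uses elsewhere |

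Every related rule treats the second class as everyone not in the first. Only the sentence that defines 'others' does not.

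**Step 4: which outputs change.** Tables 1.5 and 1.5.1 take the class from 10.1. Lists 1.4 and 1.4.1 carry the flag "patients deviated from the administration of Humira", which is defined from the conditions and not from the class, so it stays correct. Under the literal rule those lists would flag D patients as deviating, while Table 1.5 would count only F as 'others'.

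**The case against.** The best counter-argument is that the meaning can be recovered. The deviation flag, the two strata in SAP 11 and the dose-by-dose reason look-ups all point to the complement. A programmer who read them together would probably code it that way. If the literal rule were coded, the error would be easy to see: a two-row table that does not add up, with an 'others' row that may be nearly empty. The documents do not show what was programmed, and the number of affected patients is unknown and could be zero.

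Most of this stands. The intent is clear, the effect depends on literal programming, and no wrong table has been shown. It limits the severity but does not remove the defect. Table 1.5 refers to the classes in 10.1 and not to SAP 11, and the surrounding rules contradict the operative sentence without replacing it. The protocol (section 12) entrusts statistical analysis to an outside party, which should not have to overrule an explicit derivation by inference. Clear intent makes the correction safe to make; it does not make it unnecessary.

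**Conclusion.** The rule is wrong as written, and the severity is minor. If it is coded literally, every patient who misses one to three conditions is unclassed. Table 1.5 then falls short by between D − G and D patients in each group, and Table 1.5.1 omits those patients' reasons. The logic is certain. Whether any output is wrong depends on how the rule was programmed and on how many patients departed from the regimen, and the documents give neither. The effect is confined to one descriptive table and one listing. Deviating patients remain identifiable in lists 1.4 and 1.4.1. No test, adverse-reaction incidence or remission rate changes.

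**What to change.** In SAP 10.1, replace the rule for the second class with: *If at least one of [1] to [4] is not satisfied, aggregate as 'others'.* Leave conditions [1] to [4] as they are. The class then matches the dosing-deviation flag and the two strata in SAP 11, and the reason look-up reaches every patient who departed from the regimen. The sponsor should also confirm which rule was programmed.

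The cost is one sentence and, only if the code follows the present wording, a small change for Tables 1.5 and 1.5.1. No new data are needed. In that case the 'others' row and the reason list grow; no flag or other table changes. How to class patients who stop before the second or third dose is a separate question for the sponsor, and this change does not settle it.
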